8.1.6. I-OOL Score

- Summary statistics for the total score (at the time of enrollment in the treatment period, and Weeks 4 and 8 of treatment) and change (Weeks 4 and 8 of treatment) from baseline at each time point will be calculated.
- Summary statistics for the domain score (at the time of enrollment in the treatment period and Weeks 4 and 8 of treatment) and change (Weeks 4 and 8 of treatment) from baseline at each time point will be calculated.
- For the change in the total score from baseline to each evaluation time point (Weeks 4 and 8 of treatment), student's t-test will be conducted using the placebo group as the control.
- For the change in the domain score from baseline to each evaluation time point (Weeks 4 and 8 of treatment), student's t-test will be conducted using the placebo group as the control.

8.1.7. Mean Frequency of SUI Episode per 24 Hours

Of urinary incontinence episodes documented in the Bladder diary, those excluding episodes because of "Leaks irrepressibly" will be used for following analyses.

- Summary statistics for the observed value (Weeks 4 and 8 of treatment), percent change (Weeks 4 and 8 of treatment) from baseline, and change (Weeks 4 and 8 of treatment) from baseline at each time point will be calculated.
- For percent changes (Weeks 4 and 8 of treatment) and changes (Weeks 4 and 8 of treatment) from baseline to each time point of evaluation, student's t-test, Wilcoxon's rank sum test, and van Elteren test using allocation adjustment factors and age (< 60 years and ≥ 60 years) as strata will be conducted using the placebo group as the control. If any stratum includes a group with 0 patient, the test will be conducted by excluding age from the strata. The van Elteren test will be performed in two patterns, i.e., a pattern in which allocation adjustment factors at the time of enrollment are used as strata (analysis in the FAS only) and a pattern in which allocation adjustment factors recorded in CRF are used as strata.
- For percent change and changes from baseline at each week, MMRM is performed using treatment groups, evaluation time points (Weeks 4 and 8 of treatment), and interactions between the treatment group and the evaluation time point as fixed effects, and allocation factors (status of urinary incontinence, mean IEF per 24 hours [≥ 2 per day or < 2 per day]) and age (≥ 60 years or < 60 years) as covariates. Thus, the least mean square (LS Mean) in each treatment group and the difference in LS Mean between each dose group and the placebo group and the two-sided 95% CI are estimated at overall evaluation time points. Unstructured covariance structure will be assumed, and the toeplitz type will be used in case of no convergence. If convergence is still not achieved, the First-order autoregressive → Compound symmetry → Variance component will be used in this order. The Kenward-Roger method (2009)⁴⁾ will be used to calculate degrees of freedom.
- The percentage of patients with at least 50% reduction from baseline at each time point (Weeks 4 and 8 of treatment) and its 95% confidence interval (CI) will be calculated, and Fisher's exact test with placebo as the control will be conducted.

8.1.8. Mean Frequency of UUI Episode per 24 Hours

Of urinary incontinence episodes documented in the Bladder diary, those excluding episodes because of "Leaks when you do physical movements such as coughing, laughing, sneezing, standing, or doing sports" will be used for following analyses.

- Summary statistics for the observed value (Weeks 4 and 8 of treatment), percent change (Weeks 4 and 8 of treatment) from baseline, and change (Weeks 4 and 8 of treatment) from baseline at each time point will be calculated.
- For percent changes (Weeks 4 and 8 of treatment) and changes (Weeks 4 and 8 of treatment) from baseline to each time point of evaluation, student's t-test, Wilcoxon's rank sum test, and van Elteren test using allocation adjustment factors and age (< 60 years and ≥ 60 years) as strata will be conducted using the placebo group as the control. If any stratum includes a group with 0 patient, the test will be conducted by excluding age from the strata. The van Elteren test will be performed in two patterns, i.e., a pattern in which allocation adjustment factors at the time of enrollment are used

as strata (analysis in the FAS only) and a pattern in which allocation adjustment factors recorded in CRF are used as strata.

- For percent change and changes from baseline at each week, MMRM is performed using treatment groups, evaluation time points (Weeks 4 and 8 of treatment), and interactions between the treatment group and the evaluation time point as fixed effects, and allocation factors (status of urinary incontinence, mean IEF per 24 hours [≥ 2 per day or < 2 per day]) and age (≥ 60 years or < 60 years) as covariates. Thus, the least mean square (LS Mean) in each treatment group and the difference in LS Mean between each dose group and the placebo group and the two-sided 95% CI are estimated at overall evaluation time points. Unstructured covariance structure will be assumed, and toeplitz type will be used in case of no convergence. If convergence is still not achieved, the First-order autoregressive → Compound symmetry → Variance component will be used in this order. The Kenward-Roger method (2009)⁴⁾ will be used to calculate degrees of freedom.
- The percentage of patients with at least 50% reduction from baseline at each time point (Weeks 4 and 8 of treatment) and its 95% confidence interval (CI) will be calculated, and Fisher's exact test with placebo as the control will be conducted.

8.1.9. Analyses Based on Allocation Factors

Following analyses will be performed in PPS:

- Secondary endpoints will be analyzed by status of urinary incontinence (SUI, MUI) (8.1.1 to 8.1.8).
- Secondary endpoints will be analyzed (8.1.1 to 8.1.8) by mean IEF per 24 hours (≥ 2 per day, < 2 per day).

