##### 13.1.2.2 Criteria for Handling of Patient Data

The criteria for handling of patient data in the study are described below.

For problematic cases the Sponsor and the Medical Experts will discuss and determine an approach prior to database lock.

- (1) Handling of missing values and abnormal values
  - Handling of missing values in efficacy endpoints is specified for each analysis.
  - Missing values in safety endpoints are not imputed. The proportion including that of subjects with adverse events is calculated using the analysis population as the denominator for the observation period and using the number of subjects who took the study drugs for the treatment period at least once among those in the analysis population as the denominator for the treatment period.
  - The analyses will include all measured data unless the laboratory tests (eg, the effect of hemolysis during blood collection, showed obvious abnormal values). If abnormal values are excluded from the analysis, they should be specified and the reasons for exclusion should be stated.
- (2) Handling of data of patients treated by study drug different from the assigned one
  - In the analysis of the subjects treated with the study drugs or PPS, the data of patients treated with the study drug of the treatment group different from the group they are allocated to are handled as the data of the treatment group for the study drug they actually received.
  - In the analysis of FAS, the data of these subjects are handled as the data in the allocated group.

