### 13.1.3.3 Secondary Endpoint Analysis

#### 13.1.3.3.1 Efficacy Analysis

The following analyses are performed for each treatment group in FAS and PPS.

(1) Mean number of urinary incontinence per 24 hours

- Summary statistics of measured values, rate of change from baseline and amount of change at each evaluation time point are calculated.
- The rate of change from baseline is analyzed using MMRM and the therapeutic effect of TAS-303 at all evaluation time points is estimated.
- The proportion of subjects with 50% or greater improvement in the rate of change from baseline and 95% CI at each evaluation time point are calculated.

(2) Amount of urinary incontinence by 1-hour pad test

- Summary statistics of measured values, rate of change from baseline and amount of change at each evaluation time point are calculated.
- The proportion of subjects with 2.0 g or less measured values at Week 8 of the treatment period and 95% CI are calculated.
- The proportion of subjects with 50% or greater improvement in the rate of change from baseline at Week 8 of the treatment period and 95% CI are

calculated.

- (3) Mean number of used pads per 24 hours (only in patients who used incontinence pads)
  - Summary statistics of measured values, rate of change from baseline and amount of change at each evaluation time point are calculated.
- (4) ICIQ-SF score
  - Summary statistics of total score and amount of change from baseline at each evaluation time point are calculated.
  - Summary statistics of the score for each item and amount of change from baseline at each evaluation time point are calculated.
- (5) Patient Global Impression-Improvement (PGI-I)
  - Proportion for each rating on 7-point scale at each evaluation time point is calculated.
  - Proportion of improvement (“very much better”, “much better”, “a little better”) at each evaluation time point and 95% CI are calculated.
- (6) I-QOL score
  - Summary statistics of total score and amount of change from baseline at each evaluation time point are calculated.
  - Summary statistics of the score of each area and amount of change from baseline at each evaluation time point are calculated.
- (7) Analysis by allocation factor
  - The secondary endpoints are analyzed for each condition of urinary incontinence (SUI and MUI).
  - The secondary endpoints are analyzed for each category of mean number of urinary incontinence per 24 hours (less than 2/day and 2 or more/day).
- (8) Mean number of SUI per 24 hours

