6.2.3. Allocation Adjustment Factors Used for Analysis

In analyses that use allocation adjustment factors, allocation adjustment factors recorded in CRF will be used for analyses in all treated population/PPS. Analyses in FAS will be performed in two patterns, i.e., a pattern in which allocation adjustment factors recorded in CRF are used and a pattern in which allocation adjustment factors entered in IWRS are used.

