8.1. Efficacy Analysis

Following analyses will be performed by treatment group in FAS and PPS:

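### SAP 8.1.9 restricts the allocation-factor analyses of the secondary endpoints to the PPS, although the protocol specifies FAS and PPS, so no per-dose FAS version is planned in the SAP

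*SAP*

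**What the plan says.** Protocol 13.1.3.3.1 opens with one sentence that governs all its items: "The following analyses are performed for each treatment group in FAS and PPS". Item (7) sits under it with no population of its own: "The secondary endpoints are analyzed for each condition of urinary incontinence (SUI and MUI)" and "The secondary endpoints are analyzed for each category of mean number of urinary incontinence per 24 hours (less than 2/day and 2 or more/day)".

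SAP 8.1 opens the same way: "Following analyses will be performed by treatment group in FAS and PPS". Section 8.1.9 then narrows this: "Following analyses will be performed in PPS". Its scope is every earlier endpoint section: "Secondary endpoints will be analyzed by status of urinary incontinence (SUI, MUI) (8.1.1 to 8.1.8)". The same scope is stated for baseline frequency.

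The two populations treat patients differently. Under protocol 13.1.2.2, patients who received a drug other than the assigned one are analysed in the PPS by the drug they received. For the FAS the rule is: "In the analysis of FAS, the data of these subjects are handled as the data in the allocated group". SAP 6.2.3 uses the CRF values of the factors in the PPS. For the FAS it asks for both sources: "Analyses in FAS will be performed in two patterns, i.e., a pattern in which allocation adjustment factors recorded in CRF are used", the other pattern being the values entered in IWRS.

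**The concern.** SUI/MUI status and baseline frequency are the two factors used in the minimisation (protocol 3.2.1), so subgroups defined by them, with patients kept in their allocated arms, are those the design best supports. Three of the five PPS exclusion criteria concern events after randomisation: compliance below 80%, Week 8 diary entry below 70%, and prohibited medication or therapy thought to influence efficacy. If these exclusions differ by arm within a stratum, the PPS can show an apparent difference in effect between SUI and MUI, or between lower and higher baseline frequency, that the drug did not cause. The protocol's FAS version is the check on this. Under SAP 8.1.9 that check is not planned dose by dose for any secondary endpoint, and the SAP does not say why it departs from the protocol.

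**Working it through.** No figure in the plan bears directly on this point, so the check is a comparison of texts, followed by two small calculations.

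**1. Population for the secondary endpoints by allocation factor**

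| Source | Population | Scope |
|---|---|---|
| Protocol 13.1.3.3.1, lead-in and item (7) | FAS and PPS | all secondary efficacy endpoints |
| SAP 8.1 lead-in | FAS and PPS | all efficacy analyses in 8.1 |
| SAP 8.1.9 | PPS | 8.1.1 to 8.1.8 |

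A specific statement normally overrides a general one, so a programmer following the SAP would produce PPS tables only.

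**2. Is a FAS version planned elsewhere in the SAP?**

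- 8.1.11 plans FAS and PPS results by both factors, but for mean IEF only and with 3 mg and 6 mg combined. It lists summary statistics and tests, without the MMRM or the 50% responder analysis of 8.1.1.
- 8.1.17 (leakage amount) is also analysed by both factors. It names no population, so the 8.1 lead-in would apply, but this endpoint is outside 8.1.1 to 8.1.8.
- 8.1.12, 8.1.14 and 8.1.16 include analyses by both factors, all in the PPS.

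Sections 8.1.1 to 8.1.8 make eight endpoint sections, and two factors with two levels give 4 subgroup levels, so 8 × 4 = 32 section-by-level sets. A per-dose FAS version is listed for none of them. A pooled-dose FAS version is listed for 1 of 8 sections, which is 4 of the 32 sets.

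**3. How the PPS removes early stoppers**

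Under SAP 6.1.3.1, once a modification, interruption or discontinuation is recorded, treatment-period compliance is 100 × treatment days ÷ the larger of 56 and the dosing span. A patient with 44 treatment days has at most 44/56 = 78.6% and leaves the PPS. With 45 days and a span of no more than 56, it is 45/56 = 80.4% and this criterion is passed. Protocol 4.3 allows discontinuation for adverse events (item 1) and for insufficient effect or worsening (item 8), both of which can differ by arm. The FAS keeps such patients if they have efficacy data before and during treatment.

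**4. Illustration of size (assumed inputs)**

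The documents give neither the MUI share in the trial nor the number of exclusions. Assume MUI is 20% to 30% of the planned 83 per arm: 0.20 × 83 = 16.6 and 0.30 × 83 = 24.9, so about 17 to 25 patients. Assume also that 2 to 4 of them leave one arm's PPS: 2/25 = 8% to 4/17 = 24% of that subgroup arm. These are fractions lost, not estimates of bias.

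**The case against.** The case for giving this little weight is reasonable, and much of it stands.

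- **These are exploratory analyses.** They are subgroup analyses of secondary endpoints in a phase IIa trial. The Hochberg adjustment (SAP 11.5) covers only the primary objective, and no stated decision rests on 8.1.9. Overall per-dose FAS results remain planned for 8.1.1 to 8.1.8, with both factors as MMRM covariates for mean IEF, SUI and UUI frequency. This limits the severity but does not remove the mismatch.
- **No as-allocated subgroup result at all?** A reader might infer this, but 8.1.11 gives a pooled-dose FAS check on mean IEF. SAP section 12 also leaves the full list of analyses to a Table and Figure Plan that is not among the documents. The supportable statement is that the SAP lists no per-dose FAS version.
- **Does SAP 7.4 break the protocol too?** It limits the primary endpoint by factor to the PPS, so a reader might think so. Protocol 13.1.3.2(4) names no population; the FAS and PPS statement in that section belongs to item (3). SAP 7.4 fills a gap, in line with the PPS as primary efficacy population (SAP 3.2).
- **Was there an unrecorded SAP change?** The change log has no entry for 8.1.9, but it covers only changes after version 1.0. If the restriction was there from the start, no entry would be expected. What is missing is an explanation of the difference from the protocol.
- **Does SAP 6.2.3 imply FAS subgroup tables?** Not by itself. Its FAS rule also serves the MMRM covariates and the van Elteren strata.
- **Grouping by drug received** affects only patients given the wrong drug.

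**Conclusion.** The point holds for the secondary endpoints. Protocol 13.1.3.3.1 and the SAP 8.1 lead-in specify FAS and PPS; SAP 8.1.9 plans the PPS only and gives no reason. As the SAP stands, a subgroup pattern in the PPS could not be compared with a planned per-dose FAS result for any of 8.1.1 to 8.1.8, nor with any planned FAS result by factor for 8.1.2 to 8.1.8.

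The severity is minor to moderate. Any bias would depend on how exclusions fall by arm and stratum, which the documents do not report. The conclusion assumes that 8.1.9 overrides the 8.1 lead-in and that the Table and Figure Plan does not already add the FAS tables. The FAS is also not the full randomised set, since it requires a dose and efficacy data before and during treatment. It follows allocation and avoids the PPS exclusions, but does not remove every post-randomisation selection.

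**What to change.** Change the population in SAP 8.1.9 to FAS and PPS. State that FAS patients are analysed in their allocated group and that the FAS subgroups are formed in both patterns of SAP 6.2.3 (CRF and IWRS values). The PPS can remain the primary efficacy population; the order of presentation need not change. Record the revision in the change log as restoring the protocol-specified analysis, and align the Table and Figure Plan. If the sponsor prefers to keep the restriction, record and justify it as a departure from the protocol.

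Adding the FAS to SAP 7.4 is an optional improvement for consistency, not the correction of a protocol departure.

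The cost is a wording change in 8.1.9 and one extra set of tables from existing programs (a second wording change and set if 7.4 is included). No new data are needed.

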8.1.10. Mean Incontinence Episode Frequency per 24 Hours: Subgroup Analysis

Following analyses will be performed in PPS for each subgroup specified in Table 8.

- Summary statistics for the observed value (Weeks 4 and 8 of treatment), percent change (Weeks 4 and 8 of treatment) from baseline, and change (Weeks 4 and 8 of treatment) from baseline at each time point will be calculated. Summary statistics of the mean frequency of SUI episode per week will also be calculated.
- For percent changes (Weeks 4 and 8 of treatment) and changes (Weeks 4 and 8 of treatment) from baseline to each time point of evaluation, student's t-test, Wilcoxon's rank sum test, and van Elteren test using allocation adjustment factors and age (< 60 years and ≥ 60 years) as strata will be conducted using the placebo group as the control. If any stratum includes a group with 0 patients, the test will be conducted only for the age stratum identified as a prognostic factor in the blinded review. If there is any group with 0 patient, the test will not be conducted.

Table 8 Subgroup

Item	Details of subgroup
By timing of enrollment in the treatment period: Quarters and pollen season	"January to March," "April to June," "July to September," "October to December" "January to February (pollen season)"
By timing of enrollment in the treatment period: Number of patients enrolled	Months prior to the month in which a half of the patients in the whole PPS are enrolled, Month in which a half of the patients in the whole PPS are enrolled and thereafter
Mean IEF per 24 hours at baseline (≥ 2 per day or < 2 per day) × status of urinary incontinence	"< 2 per day and SUI," "< 2 per day and MUI," "≥ 2 per day and SUI," "≥ 2 per day and MUI
By measured values in the 1 hour pad test at the time of enrollment in the treatment period	≤ 5 g, > 5 g ≤ 10 g, > 10 g ≤ 50 g, > 50 g ≤ 100 g, > 100 g > 5 g, ≤ 10 g, > 10 g, ≤ 50 g, > 50 g, ≤ 100 g
By ICIQ-F score at the time of enrollment in the treatment period	$< 6, \ge 6$ $< 13, \ge 13$ $< 19, \ge 19$ $\ge 6 \text{ and } < 13, \ge 13 \text{ and } < 19, \ge 19 \text{ and } \le 21$
By I-QOL score at the time of enrollment in the treatment period	< 65, ≥ 65 < 85, ≥ 85
By baseline mean IEF per 24 hours at the time of enrollment in treatment	< 1.5 times/day, ≥ 1.5 times/day < 2.5 times/day, ≥ 2.5 times/day < 3 times/day, ≥ 3 times/day < 3.5 times/day, ≥ 3.5 times/day < 4 times/day, ≥ 4 times/day

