2.2.2. Rationale for Sample Size Determination

The number of patients was determined, assuming that efficacy comparable to that of duloxetine can be expected based on results of nonclinical studies. Based on the mean rate of change in the number of urinary incontinence of -62.28% in the duloxetine group and -41.86% in the placebo group from data of a clinical trial of duloxetine, Yentreve clinical study results, Trial ID #6231, the difference between the TAS-303 6-mg or 3 mg group and the placebo group in the rate of change in the number of urinary incontinence, which is the primary endpoint of the present study, was assumed to be -20%. From the standard deviation of 33.73% in the duloxetine group and 32.08% in the placebo group in the above study data, the standard deviation common in two groups was assumed to be 35%. Using the two-sided significance level of the entire test of 5% and the two-sided significance level of each test of 2.5% by Bonferroni's method, when the statistical power is specified as 90% and the rate of withdrawal in the treatment period as about 5%, the number of patients necessary for confirmation of a significant difference between the TAS-303 group and the placebo group is approximately 250 (83 per group).

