7.1. Primary Analysis for Primary Objective

In PPS, the difference between the TAS-303 6 mg group and the placebo group and the difference between the TAS-303 3 mg group and the placebo group will be compared for percent change from the baseline to Week 8 in the average number of urinary incontinence episodes per 24 hours using the student's t-test with the level of significance set at two-sided 5% for the entire test. The significance level for each comparison will be adjusted by Hochberg's method³⁾, considering multiplicity

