7.4. Analyses Based on Allocation Factors

Following analyses will be performed in PPS:

- Primary endpoints will be analyzed by status of urinary incontinence (SUI, MUI).
- Primary endpoints will be analyzed by mean IEF per 24 hours (≥ 2 per day, < 2 per day).

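### SAP 8.1.10 tests each dose against placebo inside 45 overlapping subgroup levels, but neither document tests whether the effect differs between levels

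*SAP*

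**What the plan says.** SAP 8.1.10: "Following analyses will be performed in PPS for each subgroup specified in Table 8". In every level, percent change and change at Weeks 4 and 8 are tested against placebo by t, Wilcoxon and van Elteren tests. A test with an empty group is skipped. Sections 8.1.13 and 8.1.15 apply the same Table 8 levels to SUI and UUI episodes.

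Table 8 uses several cuts of one variable: five for baseline frequency, four plus three bands for the pad test, and three plus three bands for the ICIQ-SF. January-February lies inside January-March. No cut is named as the main one.

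Allocation-factor splits appear in SAP 7.4 ("Primary endpoints will be analyzed by status of urinary incontinence (SUI, MUI") and 8.1.9 ("Secondary endpoints will be analyzed by status of urinary incontinence (SUI, MUI"), each also by baseline frequency below 2 or at least 2 per day, and both in the PPS. The Protocol lists the secondary-endpoint version as item (7) of 13.1.3.3.1, under the lead sentence "The following analyses are performed for each treatment group in FAS and PPS".

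The only interaction in either document is treatment by time point in the MMRM. Multiplicity adjustment (SAP 11.5) covers the primary objective alone. The SAP change log records 8.1.10 to 8.1.17 as additions in Version 3.0, made as additional analysis.

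**The concern.** A subgroup analysis is read to learn whether the drug works better in some patients than in others. Here the tables would give a p-value against placebo in each level and nothing that compares the levels. If p<0.05 in one level and not in its complement, the cause may be a real difference, lower power in the smaller level, or chance, and the planned output cannot separate these. The nested cut points make it worse, because the most favourable cut can be picked out afterwards. The risk is a misleading exploratory message from a Phase IIa trial. The primary conclusion is not at risk.

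**Working it through.** **The plan's own sample size.** Inputs from SAP 2.2.2: "which is the primary endpoint of the present study, was assumed to be -20" (percentage points), "the standard deviation common in two groups was assumed to be 35" (percent), and "the two-sided significance level of each test of 2.5% by Bonferroni's method", with 90% power and about 5% withdrawal. The noncentral t gives 78 per group (power 90.3%). 78/0.95 = 82.1, so 83 per group and 249 in total. This matches the stated 83 and about 250.

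**Count of levels and tests in 8.1.10.**

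| Table 8 item | Levels |
|---|---|
| Quarter of enrolment (4) and pollen season (1) | 5 |
| Earlier or later half of enrolment | 2 |
| Baseline frequency × SUI/MUI | 4 |
| Pad test: 4 cuts × 2, plus 3 bands | 11 |
| ICIQ-SF: 3 cuts × 2, plus 3 bands | 9 |
| I-QOL: 2 cuts × 2 | 4 |
| Baseline frequency: 5 cuts × 2 | 10 |
| Total | 45 |

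45 levels × 2 doses × 2 measures × 2 visits × 3 tests = 1,080 p-values. If all could be run under the null, 1,080 × 0.05 = 54 would fall below 0.05 on average.

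**Same true effect in every level.** Split 78 per group into two halves of 39, with a 20-point effect and SD 35 in both, each tested at two-sided 5%.
- Noncentrality = (20/35) × √(39/2) = 2.52, so power is 70.2% in each half.
- Exactly one half significant: 2 × 0.702 × 0.298 = 0.418, about 42%.
- With a 55/23 split, power is 84.4% and 47.4%. Disagreement: 0.844 × 0.526 + 0.474 × 0.156 = 0.518, about 52%.

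This needs only the plan's effect and SD and independence of the two levels, which share no patients.

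**No effect anywhere.** A simulation used the 45 overlapping levels, both doses, all four outcomes, the three tests, the age-only fallback and the skip rule. Not in the documents, and therefore assumed: the covariate distributions and correlations, a PPS of 65, 79 or 83 per arm (110, 300 and 120 simulated trials), and strong to moderate correlation between Weeks 4 and 8.

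| Result over the three scenarios | Range |
|---|---|
| Tests that could be run (mean) | 1,004-1,016 |
| p-values below 0.05, mean | 47-57 |
| p-values below 0.05, median | 32-35 |
| At least one p<0.05, all tests | 99.1-99.7% |
| At least one p<0.05, Week 8 percent-change t-test (45 × 2 = 90) | 82-84% |
| Same, favouring TAS-303 | 53-57% |

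**What interaction tests would leave.** Joint tests over both doses, on Week 8 percent change under the same null, gave at least one p<0.05 in 51-58% of trials over the 20 partitions in Table 8 (independence: 1 − 0.95^20 = 64%). With one partition per Table 8 item, seven tests, the figure was 28-30% (1 − 0.95^7 = 30%).

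**The case against.** The strongest reply is that these analyses are exploratory and the plan claims nothing for them. They were logged as additional, SAP 10 requires analyses planned after key code breaking to be distinguished, and error control is promised only for the primary comparison, "using the student's t-test with the level of significance set at two-sided 5% for the entire test". That stands: the primary type I error is untouched, and this limits the priority of the point.

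Several stronger readings are tempting, and the documents do not support them.
- A reader might infer that effect modification will be judged by these p-values, or that they will decide who enters the next trial. The SAP gives no decision rule, and the Protocol's text on expected use (1.4.3) concerns safety, dose response and the recommended dose.
- A reader might infer that 7.4 and 8.1.9 run all three tests in each level. 7.4 says only that the endpoint is analysed by factor. 8.1.9 points to 8.1.1 to 8.1.8, where 8.1.2 to 8.1.6 have no Wilcoxon or van Elteren test. 8.1.1, 8.1.7 and 8.1.8 include an MMRM, so read literally 8.1.9 already yields per-level differences with 95% CI for the diary endpoints.
- A reader might infer that every allocation-factor split is PPS-only. SAP 8.1.11, for the pooled doses, uses FAS and PPS. For the primary endpoint, Protocol 13.1.3.2 item (4) names no population, so 7.4 does not contradict it. The mismatch is confined to 8.1.9.
- A false finding is near certain only over all tests, both visits and either direction.

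The count is also a ceiling. Empty groups are skipped, the pad-test row is read from a flattened table, and if 21 is the top ICIQ-SF score, two levels coincide and 44 × 24 = 1,056 remain.

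None of this supplies the missing comparison between levels. An exploratory label does not make within-level p-values informative about a difference.

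**Conclusion.** The point holds as a defect in exploratory analyses. As planned, the Table 8 tests cannot distinguish a differing effect from unequal power or chance. Even with an identical effect at the planned size, two equal halves disagree on significance in about 42% of trials. That figure rests only on the plan's effect and SD and on 78 evaluable patients per group.

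The null percentages (about 99% over all tests, 82-84% for the Week 8 percent-change t-test, 53-57% favouring TAS-303) depend on assumed covariate distributions and modest simulation runs, and should be read as approximate. The count of 45 levels and at most 1,080 p-values does not depend on them.

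The difference in population between SAP 8.1.9 and Protocol 13.1.3.3.1 is a separate, smaller inconsistency, and the change log gives no reason for it.

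**What to change.** - For the allocation factors and each Table 8 item, fit the MMRM with treatment-by-visit-by-factor terms and their lower-order terms, or define a Week 8 contrast. A treatment-by-factor term alone would average over Weeks 4 and 8 and miss the primary time point.
- Report one Week 8 interaction p-value per factor, joint over both doses, and the dose-minus-placebo difference with 95% CI in each level. Drop the within-level p-values.
- Name one main cut point per variable, or use baseline frequency, pad weight, ICIQ-SF and I-QOL as continuous modifiers. Keep the other cuts descriptive.
- Label all of it exploratory and without multiplicity control, and state the residual risk: about a 28-30% chance of at least one false positive over seven factors. Testing the two allocation factors separately as well makes nine, with an independence figure of 1 − 0.95^9 = 37%.
- Run 8.1.9 in the FAS as well as the PPS, to agree with the Protocol.

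Cost: SAP wording and modest programming, no new data, and fewer tables overall. The downside is that interaction tests have low power. In the 39-per-group example, the standard error of one half's difference is 35 × √(2/39) = 7.9 points, and that of the difference between halves is 7.9 × √2 = 11.2 points. A non-significant interaction is therefore not evidence that the effects are equal. Cheap improvement.
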